### **6.8.4 Electrocardiogram (ECG) Parameters**

ECG Parameters include collected and derived qualitative parameters. Qualitative parameters will be summarized by absolute counts (n) and percentages (%). Percentages will be based on the number of patients with data.

### **6.8.5 Vital Signs**

Vital Signs include collected and derived continuous and categorical variables. Continuous variables will be summarized by the number of patients, mean, SD, median, minimum and maximum values. Categorical variables will be summarized by absolute counts (n) and percentages (%). Percentages will be based on the number of patients with data.

### **6.8.6 Physical Examination**

Routine physical examination results will be listed for individual patients.

### **6.8.7 HAE attacks**

Individual patient listings will be presented for the date and location of HAE attacks.

### **6.8.8 Immunogenicity**

Descriptive statistics will be presented at each assessment time, by attack. In addition, summaries will be presented for anti-rhC1INH IgG, anti-rhC1INH IgM and anti-HRI, by attack, for Presentation, Day 28 and Day 90 for the following categories:

- Initial assay “below cut-off”
- Initial assay “above cut-off” but confirmatory assay missing
- Confirmatory assay did not confirm initial result
- Confirmatory assay confirmed initial result

The total number of patients assessed for each antibody will also be summarized by attack and timepoint. Confirmatory assays here include displacement assays for anti-rhC1INH IgG, anti-rhC1INH IgM and anti-HRI and the neutralizing assays for anti-C1INH and anti-rhC1INH.

Separate listings will be produced for the initial assay results and for the confirmatory assay results. Those patients with a confirmed positive result will be highlighted in two further listings (again one for initial and one for confirmatory).

## **6.9 Other Analyses**

### **6.9.1 Diagnostic Assays and IgE Testing**

Descriptive statistics will be presented for the Safety Analysis Set. In particular, a summary will be presented of C1INH, C1q and C4 at Screening and separately of C4 at Presentation.

A shift table of anti-rabbit epithelium IgE results will be presented to indicate the change from Screening to Day 28 of each attack. A negative test for anti-rabbit epithelium has a cut off of <0.35 kU/L and so the shift table will summarize the categories (“Below or equal to 0.35 kU/L” and “Above 0.35 kU/L”).

All individual patient diagnostic and IgE assay results will also be listed.

All values below the limit of quantification (BLQ) for C1INH, C1q and C4 will be set to half the value of the lower limit of quantification (LLQ) for calculation of summary statistics. Similarly, all IgE results BLQ will be set to half the value of LLQ for categorization used in the shift table.

However, in the listings all BLQ values will be reported as “<LLQ”, where LLQ will be replaced with the corresponding value for the LLQ of the parameter.

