10 METHODS

10.1 Study parameters

10.1.1 Main study parameter

The primary objective is the assessment of safety and tolerability.

This will be evaluated by recording of adverse events (spontaneously reported by the patient or observed by the investigator).

Immunogenicity (for all attack treatments) will be evaluated by the following parameters:

- antibodies against host related impurities (anti-HRI)
- antibodies against recombinant human C1INH (IgG and IgM) anti-rhC1INH)
- IgE antibodies against rabbit epithelium (anti rabbit epithelium IgE)

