These tests and antibody assays mentioned above will be performed by QPS Netherlands B.V.

- C1INH activity will be determined as inhibitory activity against C1 esterase with a chromogenic assay.
- C1q assays will be performed by nephelometry. This assay will be performed at screening to confirm the diagnosis of HAE and/or to exclude AAE.
- Levels of C4 antigen will be determined by nephelometry. This will be performed at screening and at baseline of each attack to support the diagnosis of HAE.
- Anti-rabbit epithelium (dander) and anti-cow milk IgE assays will be performed using a validated, commercially available system⁽⁸⁾ (ImmunoCAP®, Phadia, Sweden; or equivalent. Prior to treatment with Ruconest a negative test for anti-rabbit epithelium (dander) (cut off <0.35 kU/L) should be documented. Anti-cow milk IgE will be tested once at screening. Anti-rabbit epithelium (dander) IgE will be performed at screening, at the Day 28 follow-up visit of each attack, every year following screening, and if adverse events are observed indicative of hypersensitivity reactions.

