Independent of the occurrence of eligible acute HAE attacks, a center visit is scheduled at every year (\pm 1 month) after screening at which the following procedures are scheduled:

- blood sampling for IgE antibodies against rabbit epithelium
- HAE history since previous visit, if applicable (e.g. occurrence of intercurrent HAE-episodes etc)
- record and assess new AE/SAE's or changes to ongoing AE/SAE's since the last visit, if applicable
- record changes in concomitant medication

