### **4.3 Other Measures**

#### **4.3.1 Diagnostic Assays and IgE Testing**

Blood samples for diagnostic assays will be collected at screening. The samples will be analyzed for the following parameters: C1INH activity, C1q, C4 and C1INH auto antibodies (IgM, and IgG anti-rhC1INH).

Assays for IgE antibodies against rabbit epithelium (anti-rabbit epithelium IgE [dander]) will be performed at screening, at Day 28 after each attack, every year following screening and if AEs indicative of a hypersensitivity reaction are observed. Prior to treatment with Ruconest a negative test for anti-rabbit epithelium (dander) (cut off <0.35 kU/L) should be documented.

Similarly, assays for IgE antibodies against cow milk (anti-cow milk IgE) will be performed once at Screening.

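### The only IgE table stops at Day 28, so a conversion first found at a yearly or event-triggered test can be missing from the summary of a main safety parameter

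*SAP*

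**What the plan says.** **Status of the parameter.** Protocol 10.1.1 (Main study parameter) includes anti-rabbit epithelium IgE among the immunogenicity measures. SAP 4.2 names it again under the primary safety objective.

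**When it is tested.** SAP 4.3.1 has the assay "performed at screening, at Day 28 after each attack, every year following screening and if AEs indicative of a hypersensitivity reaction are observed". Protocol 10.2.1.3 gives the same occasions, ending with "every year following screening, and if adverse events are observed indicative of hypersensitivity reactions". Protocol 10.2.4.3 schedules a yearly centre visit whether or not an attack has occurred, and its first procedure is "blood sampling for IgE antibodies against rabbit epithelium".

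**What is tabulated.** SAP 6.9.1 plans a shift table of the IgE results "to indicate the change from Screening to Day 28 of each attack". The lower category of that table is "Below or equal to 0.35 kU/L". The same section says that all individual IgE results will be listed.

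**The concern.** There are three kinds of post-screening IgE test: Day 28, yearly and event-triggered. Only the first feeds a table. The protocol describes allergic reaction to host-related impurities as the only significant clinical risk known so far (9.4.1), and repeat treatment depends on the IgE test staying negative (section 6). A reader of the study report will look to the shift table for the number of children who converted. If the one conversion was found at a yearly or unscheduled test, the table can show none, with nothing to indicate that other results exist. The number would have to be pieced together from a listing that carries no denominator and no interval.

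**Working it through.** The documents give no figure on this point to reproduce. The check sets the test occasions beside the planned outputs, and then adds an illustration of scale.

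**Step 1. Test occasions against outputs**

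| IgE test occasion | Source | In a table? | In a listing? |
|---|---|---|---|
| Screening | Protocol 10.2.1.3; SAP 4.3.1 | Yes, as the starting point of Table 14.3.4.7 | Yes |
| Day 28 of each attack | Protocol 10.2.1.3; SAP 4.3.1 | Yes, Table 14.3.4.7 | Yes |
| Yearly after screening | Protocol 10.2.1.3 and 10.2.4.3; SAP 4.3.1 | No | Yes |
| After a suspected hypersensitivity event | Protocol 10.2.1.3; SAP 4.3.1 | No | Yes |

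**Step 2. Does another output close the gap?**
- SAP 6.8.8 gives categorical summaries for anti-rhC1INH IgG, anti-rhC1INH IgM and anti-HRI at Presentation, Day 28 and Day 90. IgE is not among them. Protocol 12.3.3 likewise leaves IgE out of its immunogenicity analysis.
- SAP 6.9.1 opens with a general promise of descriptive statistics, but Attachment 1 contains no IgE table other than 14.3.4.7. The two remaining diagnostic tables (14.3.4.6.1 and 14.3.4.6.2) are for Screening and Presentation.
- Table 14.3.2.3 counts adverse events of special interest. It does not count IgE status, so a conversion without symptoms is absent from it.

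**Step 3. Which conversions are missed?**
- First found at a yearly visit after the child's last Day 28 sample: missed. Protocol section 6 allows further treatment only while the test is negative, so no later attack can supply a Day 28 result.
- First found at an event-triggered test, with no later positive Day 28 result: missed.
- First found at an event-triggered test and still present at a Day 28 sample: not missed, because the Day 28 result shows it.

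**Step 4. Scale (illustration)**
The assumption is 20 treated children, the minimum target in SAP 2.3, each with an evaluable result. The intervals are Clopper-Pearson 95% intervals.
- 0/20: upper limit = 1 − 0.025^(1/20) = 16.8%; the interval is 0 to 16.8%.
- 1/20 = 5%: lower limit = 1 − 0.975^(1/20) = 0.1%; upper limit = the 97.5% point of Beta(2, 19) = 24.9%.
- 2/20 = 10%: the 2.5% point of Beta(2, 19) and the 97.5% point of Beta(3, 18) give 1.2% to 31.7%.

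**Step 5. The 0.35 kU/L boundary**
- Protocol 7.3 treats a value above 0.35 as positive, so exactly 0.35 is not positive.
- Protocol 10.2.1.3 and SAP 4.3.1 give the cut-off for a negative test as below 0.35, so exactly 0.35 is not negative.
- SAP 6.9.1 states the negative cut-off as below 0.35 and, in the same sentence, derives a category that includes 0.35.

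Only a result of exactly 0.35 changes category.

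**The case against.** The best defence is that nothing is lost. Every IgE result is listed, the study is descriptive with no hypothesis tests (SAP 5.2), and with about 20 children a single positive can be found by reading the listing. That stands, and it limits the point to the summary. It does not remove it, because a table that carries a main parameter should not show zero when the data contain a positive.

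Several stronger readings are tempting, and the documents do not support them.

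- *A child who converts and reacts would be visible only in a listing.* A reaction starting within 97 days of a dose is a treatment-emergent event under SAP 4.2.2.1 and is counted in the adverse event tables. If serious, it is in the serious event table. If non-serious, a type I reaction due to newly formed anti-rabbit IgE is a named event of special interest with its own table. Only the IgE value is confined to the listing.
- *Event-triggered conversions never reach the table.* Protocol 10.5 completes the Day 28 visit of withdrawn patients where possible, so a conversion that persists until then is tabulated.
- *Event-triggered tests are the ones most likely to be positive.* This is plausible, but the documents give nothing to show it.
- *A large share of Day 28 tests will be lost because re-treatment resets the visit.* The reset is real (protocol section 6), but its size depends on a treated-attack rate that the documents do not give. With a Poisson rate r per year, the chance of a new treatment within 28 days is 1 − exp(−28r/365): 7% at r = 1, 21% at r = 3, 37% at r = 6 and 60% at r = 12. A reset also postpones the sample to the latest attack, and the last treated attack is not superseded. A wider summary cannot recover samples that were never taken, so this is not part of the case.
- *The SAP categories contradict the protocol's cut-off.* They agree with protocol 7.3 and disagree with protocol 10.2.1.3. The conflict starts inside the protocol.

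**Conclusion.** The point holds in a limited form. Two of the three kinds of post-screening IgE test enter no table, although IgE is a main safety parameter. Table 14.3.4.7 can therefore understate conversions when the first positive comes at a yearly visit after the last Day 28 sample, or at an unscheduled test with no later positive Day 28 result. This conclusion rests on the text alone. The contrast between 0/20 and 1/20 assumes 20 evaluable children and exactly one such conversion. It shows scale and does not predict a result. The documents do not suggest that clinical reactions would go uncounted or that data would be lost. The boundary inconsistency is a separate and minor matter.

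**What to change.** 1. Keep the Day 28 columns of Table 14.3.4.7 and add one per-patient row: the highest IgE category after first dose at any Day 28, yearly or event-triggered test. Give n/N and an exact 95% interval, where N is the number of treated children with at least one IgE result after first dose.
2. Reconcile the 0.35 kU/L boundary across protocol 7.3, protocol 10.2.1.3, SAP 4.3.1 and SAP 6.9.1, and align the table categories with the outcome. This review does not say which form is right, because the same boundary governs eligibility.

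The cost is a sentence in SAP 6.9.1 and one table row, from results already scheduled for collection. Yearly visits already have output labels (SAP Table 2). The attached SOP deviation form says that the analysis has been finalised. In that case the row can be given as a supplementary table, described and justified in the study report, which is the route that SAP 7.5 provides for changes after database lock.

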## 6.9.2 PK and PD Assays

A series of blood plasma samples will be taken for the analysis of C1INH and C4 activity at the following time points relative to a patient's first attack and dosing: Presentation, 5 minutes and 2-4 hours (post-dose). Additionally, for the first attack, PK parameters will be calculated and presented for C1INH activity.

### 6.9.2.1 PK and PD Concentrations

To assess the single dose PK and PD profiles, PK and PD concentrations will be listed, summarized and plotted for patients in the PK/PD Concentration Set, where missing and BLQ values will be handled as detailed in Section 6.9.2.1.1.

Functional C1INH (PK) concentrations will be in units of % of Normal (i.e. results are expressed as a percent based on a pool of plasma collected from healthy volunteers, which was original set at 100%) whereas C4 concentrations will be in units of  $\mu\text{g}/\text{mL}$ .

The Baseline concentration is defined as the concentration taken at Presentation.

Summaries and figures will include:

- Listing of all PK and PD concentrations sorted by, patient ID and nominal time post-dose. The listings of concentrations will include the actual sample collection times, the time of dosing and deviations from the nominal time.
- A summary of concentrations by nominal time post-dose, where the set of statistics will include n, mean, geometric mean, median, SD, coefficient of variation (CV) Geometric CV, minimum, maximum and the number of concentrations above the LLQ.
- Boxplots of concentrations paneled by nominal time, presented separately on linear and logarithmic scales.
- Boxplots of concentrations grouped by weight and paneled by nominal time, presented separately on linear and logarithmic scales.
- The ratio (2-4 hours:Baseline) in C4 versus the ratio (2-4 hours:Baseline) in Functional C1INH.

The subgroups for weight for the boxplots of concentrations will be:

- 1) Weight  $\leq 30\text{kg}$
- 2)  $30\text{kg} > \text{Weight} \geq 60\text{kg}$

- 3) 60kg > Weight  $\geq$  84kg
- 4) Weight > 84kg

Paneling by weight will only be performed if there are a sufficient number of patients in each subgroup.

The range for the x-axes of these plots will be decided on review of the data, and will depend on how long the concentration is quantifiable in the matrix.

For summary statistics and boxplots by sampling time, the nominal PK/PD sampling time will be used.

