7.2 Inclusion criteria

Screening

- From 2 up to and including 13 years of age
- Clinical and laboratory confirmed diagnosis of HAE (baseline C1INH activity <50% of normal)
- Signed written informed consent (parental permission) signed by the legal guardian(s)

Treatment

- Clinical symptoms of an acute HAE attack
- Onset of eligible symptoms within 5 hours from the moment at which medical evaluation to determine eligibility has occurred
- IS score for at least one anatomical location at the time of initial evaluation of at least 3 (moderate severity or greater) without signs of spontaneous regression
- 24h or more have passed since the patient's last study treatment

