10.2.2 Blood sampling procedures and parameters

It is recommended, for the sake of patient's comfort, to use butterfly needles and to place a catheter during the time of hospitalization for easy blood collection. Also, applying a topical anesthetic before catheter placement may be considered.

For central laboratory testing, the amount of blood taken per patient has been carefully considered, to reduce the burden as much as possible. For diagnostic testing, PK/PD analyses, and immunology testing, depending on the need, either 1.8, 2.7 or 4.5 mL of venous blood will be collected at the designated time points (see below and Appendix A), i.e. by using the smallest citrate-tube available. The routine laboratory safety parameters will be assessed in the local laboratories, and the required blood volume may vary between laboratories. At the set-up of the study, special attention will be given to minimize the required blood volume for this routine safety testing. The estimated volumes below are considered the maximally required sample volumes based on 5 mL collection tubes.

The typical amount of blood taken from a patient including a screening visit and following one HAE attack during the 90-day follow-up period will be a maximal volume of 30 mL according to the schedule below (see also appendix A). If subsequent attacks will be treated with the study medication, where PK/PD sampling is no longer scheduled, the volume of blood collection during the treatment period is estimated to account for a maximal volume of 25 mL for each additional attack.

If a 2 year old child was followed up for a single HAE attack (assuming an otherwise healthy child with a weight of 12 kg, and a whole blood volume of 80 mL/kg BW) the total volume of removed blood over a 3 month period would account for $30/960=3.1\%$ of total blood volume. For a 13 year old (assuming an average weight 44 kg and a whole blood volume of 75 ml/kg BW) this would be

Safety of Ruconest in 2-13 year old HAE patients

under 1%. It is generally accepted that blood loss should not exceed 3% of total blood volume over four weeks, and it should not exceed 1% of total blood volume at any single time⁽⁹⁾. In case of doubt, the investigator should ascertain that the hematocrit is not less than 38 volume%⁽¹⁰⁾.

| Blood sampling volumes | Screening | First Attack | Subsequent attacks |

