**Quanticate**  
The Clinical Data Experts

Table Number	Title	Analysis Set	Repeat
	(TEQ)		Figure 14.2.1.1.1
Figure 14.2.1.7	Kaplan Meier Plot of Time to Complete Resolution	ITT	Repeat of Figure 14.2.1.1.1
Figure 14.2.1.8.1	Bar Chart of Therapeutic Failure for First Attack	ITT	Unique
Figure 14.2.1.8.2	Bar Chart of Therapeutic Failure for Last Attack	ITT	Repeat of Figure 14.2.1.9.1
Figure 14.2.2.1.1	Boxplot of Functional C1INH (% of Normal) paneled by Time (Linear Scale)	PK/PD Concentration Set	Unique
Figure 14.2.2.1.2	Boxplot of Functional C1INH (% of Normal) paneled by Time (Logarithmic Scale)	PK/PD Concentration Set	Repeat of Figure 14.2.2.1.1
Figure 14.2.2.1.3	Boxplot of Functional C1INH (% of Normal) grouped by Weight and paneled by Time (Linear Scale)	PK/PD Concentration Set	Unique
Figure 14.2.2.1.4	Boxplot of Functional C1INH (% of Normal) grouped by Weight and paneled by Time (Logarithmic Scale)	PK/PD Concentration Set	Repeat of Figure 14.2.2.1.3
Figure 14.2.2.2.1	Boxplot of C4 Concentrations paneled by Time (Linear Scale)	PK/PD Concentration Set	Unique
Figure 14.2.2.2.2	Boxplot of C4 Concentrations paneled by Time (Logarithmic Scale)	PK/PD Concentration Set	Repeat of Figure 14.2.2.2.1
Figure 14.2.2.2.3	Boxplot of C4 Concentrations grouped by Weight and paneled by Time (Linear Scale)	PK/PD Concentration Set	Unique
Figure 14.2.2.2.4	Boxplot of C4 Concentrations grouped by Weight and paneled by Time (Logarithmic Scale)	PK/PD Concentration Set	Repeat of Figure 14.2.2.2.3
Figure 14.2.3	Ratio with respect to Baseline in C4 versus Ratio with respect to Baseline in Functional C1INH	PK/PD Concentration Set	Unique

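### The SAP's weight bands for the PK/PD figures exclude every child above 30 kg and up to 84 kg, and its condition that each band be filled would very probably fail even with the signs corrected

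*SAP*

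**What the plan says.** SAP 6.9.2.1 (PK and PD Concentrations) plans "Boxplots of concentrations grouped by weight and paneled by nominal time, presented separately on linear and logarithmic scales". It then introduces four bands with "The subgroups for weight for the boxplots of concentrations will be". In plain notation they are:

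1. weight ≤ 30 kg
2. 30 kg > weight ≥ 60 kg
3. 60 kg > weight ≥ 84 kg
4. weight > 84 kg

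The next sentence sets the condition: "Paneling by weight will only be performed if there are a sufficient number of patients in each subgroup". No minimum number is given.

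SAP Attachment 1 lists four by-weight figures, 14.2.2.1.3 and 14.2.2.1.4 for C1INH and 14.2.2.2.3 and 14.2.2.2.4 for C4. The first is titled "Boxplot of Functional C1INH (% of Normal) grouped by Weight and paneled by Time (Linear Scale)". None carries the condition.

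On the population, Protocol 7.2 admits patients "From 2 up to and including 13 years of age" and sets no weight limit. Protocol 10.2.2 uses 12 kg for a 2-year-old and gives the other end as "For a 13 year old (assuming an average weight 44 kg and a whole blood volume of 75 ml/kg BW)". SAP 2.3 targets at least 20 treated patients, and PK/PD samples are taken at the first attack only. Protocol 8.1 has a separate dosing rule from 84 kg upwards, and SAP 6.8.1 splits the exposure summary at the same point, with exactly 84 kg in the upper category.

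**The concern.** Dosing is per kilogram, so whether C1INH and C4 levels look alike across body sizes is a natural question for these data. The four by-weight boxplots are the only PK/PD outputs in Attachment 1 broken down by body size. SAP 5.3 allows no covariates, and SAP 7.1 cuts the PK parameters to Cmax and AUC0-3.

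Two of the bands cannot hold anyone, and the rule for making the display needs all four to be filled. A programmer would have to decide, with the data in hand, what the bands were meant to be, what number is sufficient, and whether the text or the figure list governs. Those choices belong in the plan.

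**Working it through.** The documents state no figure to reproduce here; the target of 20 rests on feasibility.

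**Step 1: the bands as written.** Band 2 needs weight < 30 and weight ≥ 60 together, and band 3 needs weight < 60 and weight ≥ 84 together. Both are empty sets. On a 0.1 kg grid from 8 to 130 kg, bands 1 to 4 contain 221, 0, 0 and 460 grid points, and the weights in no band run from 30.1 to 84.0 kg. The protocol's 12 kg child falls in band 1; its 44 kg 13-year-old falls in none. With two empty bands, a sufficient number in each is unattainable whatever the data.

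**Step 2: signs reversed.** Reading the middle bands as 30 < weight ≤ 60 and 60 < weight ≤ 84 puts every weight in exactly one band, with 44 kg in band 2. Exactly 84 kg then falls in band 3, whereas the exposure summary places it in the upper category.

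**Step 3: would the corrected bands fill?** The documents give two planning weights and no spread, so the following are assumptions:
- Mean weight is linear in age a, from 12 kg at 2.5 years to 44 kg at 13.5 years: m(a) = 12 + 32 × (a − 2.5)/11.
- Weight is lognormal with coefficient of variation CV: σ² = ln(1 + CV²), μ = ln m(a) − σ²/2.
- Ages are uniform, either over the whole range (2 to under 14) or over an older mix (10 to under 14). The older mix allows for the mean age at onset of 11.2 years in Protocol 4.1.

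With p the age-averaged probability of exceeding 84 kg, the expected count is 20p and the chance of at least one is 1 − (1 − p)^20.

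| Ages | CV | ≤30 | >30–60 | >60–84 | >84 | Chance of any >84 |
|---|---|---|---|---|---|---|
| 2–13 | 15% | 11.5 | 8.4 | 0.04 | 0.00 | about 0 |
| 2–13 | 30% | 12.3 | 7.3 | 0.44 | 0.03 | 3% |
| 2–13 | 40% | 12.6 | 6.5 | 0.70 | 0.13 | 12% |
| 10–13 | 15% | 1.3 | 18.6 | 0.11 | 0.00 | about 0 |
| 10–13 | 30% | 4.5 | 14.2 | 1.2 | 0.09 | 9% |
| 10–13 | 40% | 6.1 | 11.8 | 1.8 | 0.36 | 30% |

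Counts are expected numbers among 20 children. The two middle columns together are the children with no band as the SAP is written: about 7 to 8 of 20 under the full age range and 14 to 19 of 20 under the older mix.

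**Step 4: a deliberately extreme case.** Take all 20 as 13-year-olds with mean 44 kg and SD 18 kg.
- Lognormal: σ² = ln(1 + (18/44)²) = 0.155, σ = 0.393, μ = 3.784 − 0.077 = 3.707. z = (ln 84 − 3.707)/0.393 = 1.84, so p = 0.033. Expected 20p = 0.66; chance of at least one 1 − 0.967^20 = 49%; chance of at least three 2.7%.
- Normal: z = (84 − 44)/18 = 2.22, p = 0.013. Expected 0.26; chance of at least one 23%.

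Even here fewer than one child is expected in the top band.

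**Step 5: text against figure list.** SAP 6.9.2.1 makes paneling by weight conditional, while Attachment 1 lists the four figures outright. The condition speaks of paneling by weight, but the figures are grouped by weight and paneled by time, so its reach is unclear.

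**The case against.** The reversed signs look like a slip. The cut points 30, 60 and 84 run in order, and a competent programmer would read the middle bands as 30 to 60 and 60 to 84. That is fair, but it repairs only Step 1. The all-bands condition and the mismatch with Attachment 1 remain.

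A reader might infer that the bands contradict the eligible population. The documents do not support that. Entry sets no weight limit, treatment beyond age 13 is allowed, and the 84 kg cut mirrors a category that both the dosing rule and the exposure summary foresee. The empty middle bands are an inequality error, and the top band is improbable rather than impossible.

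A reader might also infer that the figures will never be made. That does not follow: sufficient is undefined, the condition may not govern figures grouped by weight, and Attachment 1 lists them unconditionally.

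Nor do the documents make body size the central PK question. The objective in Protocol 5 is to assess PK and PD in this age group, without mentioning size. A ceiling of 3% on the chance of any child above 84 kg would also be too firm, since it holds only for the full age range with CV up to 30%.

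Finally, putting a 12 kg and a 30 kg child in one band is a choice of cut point, not an error. Weight and concentrations are both listed by patient, so the relationship could be recovered by hand.

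**Conclusion.** The point stands in a limited form. Without any assumption, two of the four bands are empty sets, weights above 30 kg and up to 84 kg are unassigned, the condition cannot be met as written, and it disagrees with the figure list.

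Under the assumed ages and weight spreads, correcting the signs would very probably not rescue the condition. The band above 84 kg is expected to hold about 0.00 to 0.4 of 20 children at CV 15 to 40%, and the chance of even one runs from about 0 to 30%. These figures depend on an assumed age mix and spread that the documents do not give. The conclusion that fewer than one child is expected there survives the extreme case in Step 4.

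The consequence is confined to four descriptive figures for a secondary objective, in a study with no hypothesis tests. It is worth correcting because they are the only planned PK/PD display by body size.

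**What to change.** In SAP 6.9.2.1:
- Rewrite the bands so that they cover every weight once, for example ≤30, >30 to 60, >60 to <84 and ≥84 kg. This puts exactly 84 kg in the same category as the exposure summary in SAP 6.8.1.
- Delete the condition that every band be filled. State a minimum number per band and a rule, fixed in advance, for merging sparse upper bands downwards.
- Make Attachment 1 and the text agree on whether the figures are always produced.

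Preferably, replace or supplement Figures 14.2.2.1.3–4 and 14.2.2.2.3–4 with individual-patient plots against body weight at Presentation: C1INH and C4 at 5 minutes and at 2–4 hours, plus Cmax and AUC0-3 for C1INH. These need no cut points and can show every child with data.

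The cost is SAP wording and figure code. Weight is already recorded at Presentation (SAP 4.2.5), so nothing new is collected. If the database is already locked, SAP 7.5 provides for describing and justifying the change in the clinical study report.
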